7.4 Study Termination

Study Termination (Visit 16) will take place 24 to 32 days after the Experimental Session 3 (Visit 12) and after the last Integrative Session 3.3 (Visit 15). Participants who have withdrawn from treatment but have continued for follow-up will also complete this assessment immediately upon withdrawal.

The site team will:

- Inquire about any possible changes in health. Assess the participant's mental health and the status of any previously recorded AEs. Record AEs as described in Section 10.0 Safety.
- Inquire about concomitant medication use and adherence.
- Administer Since Last Visit C-SSRS.
- Measure weight (used to calculate BMI).
- Measure blood pressure.
- Perform urine pregnancy test for participants who are able to become pregnant.
- Provide and discuss a study Exit Plan/Plan for Moving Forward.
- Ask them to enroll into the LTFU extension study with a visit at least 6 months after the last Experimental Session. Review contact information and Informed Consent procedures for LTFU.
- Actively support participant in completion of Study Termination self-reported measures. Completion of the measures does not need to be recorded.
 - o LEC-5
 - o PCL-5, under the direction of the therapy pair, who will remind them of the index trauma listed in the parent study to which PTSD symptoms should be anchored
 - o SDS
 - o BDI-II
 - o CPGS
 - o EQ-5D-5L
 - AUDIT
 - o DUDIT
 - SRNUEAT-26
 - HPOSF

After all Study Termination measures and assessments are completed, the participant is considered terminated from the study. The participant can resume normal everyday life.

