4.4.4 Early Termination from the Study

Participants who are removed from the study after they receive IMP but do not complete the study may fall into one of these categories: Post-Treatment Early Termination or Dropout. If the participant has received IMP in at least one Experimental Session and completed one PCL-5 assessment beyond Baseline, they will be considered evaluable. All participants who receive IMP in at least one Experimental Session will be included in all safety analyses.

Participants can withdraw from treatment or withdraw consent at any time for any reason without judgment. The site team can withdraw a participant if, in their clinical judgment, it is in the best interest of the participant or if the participant cannot comply with elements of the protocol that are critical for safety or for the scientific integrity of the study. If the site team makes the decision to terminate the participant from treatment or the study, they will explain the reason for withdrawal and document in the participant's source records and Electronic Case Report Form (eCRF). If a participant develops any Exclusion Criteria that, in the opinion of the Medical Monitor or Investigators, affects the safety of the participant, including psychiatric diagnosis, medical diagnosis, pregnancy, or requirement of use of prohibited medications, the participant will discontinue treatment in Experimental Sessions but remain in the study for the associated Integrative Sessions. Any time a participant terminates from the study early, the site team will attempt to obtain information about AE outcomes if appropriate, as determined by the site physician and Medical Monitor. The site team will provide the participant with an Exit Plan/Plan for Moving Forward as described in Section 7.4.2 Exit Plan/Plan for Moving Forward.

Below are the definitions of the two types of participants who terminate the study after they receive IMP but before study completion:

- **Post-Treatment Early Termination**: Participants who discontinue study treatment but continues to participate in primary and secondary outcome assessments. Data collection will continue on the same schedule as planned through Study Termination visit procedures.

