7.3.1 Experimental Sessions

There will be three open-label Experimental Sessions (Visits 4, 8, 12). Procedures for MDMA-assisted therapy will remain the same across all sessions and all procedures regardless of dose received. Experimental Sessions must be at least 6 hours long, measured from 30 minutes prior to IMP administration. The Experimental Sessions will consist of:

- Experimental Session 1 (Visit 4) will occur 1 to 14 days after Preparatory Session 3 (Visit 3). The first Experimental Session will include 80 mg of MDMA followed by a supplemental half-dose 1.5 to 2 hours after the initial dose unless tolerability issues emerge with the first dose or it is refused by the participant.
- Experimental Session 2 (Visit 8) will occur 21 to 56 days after Experimental Session 1 (Visit 4) and 1 to 14 days after Integrative Session 1.3 (Visit 7). A dose of 80 or 120 mg MDMA will be administered. A supplemental dose (40 mg or 60 mg) will be administered 1.5 to 2 hours after the initial dose unless tolerability issues emerge with the first dose or it is refused by the participant. If the participant received an initial dose of 80 mg, a 40 mg supplemental dose will be used. If the participant received an initial dose of 120 mg, a 60 mg supplemental dose will be used. If drug supply does not permit availability of 60 mg capsules, a reduced supplemental dose of 40 mg may be administered following the 120 mg initial dose.
- Experimental Session 3 (Visit 12) will occur 21 to 56 days after the second Experimental Session (Visit 8) and 1 to 14 days after Integrative Session 2.3 (Visit 11). A dose of 80 or 120 mg MDMA will be administered. A supplemental dose (40 mg or 60 mg) will be administered 1.5 to 2 hours after the initial dose unless tolerability issues emerge with the first dose or it is refused by the participant. If the participant received an initial dose of 80 mg, a 40 mg supplemental dose will be used. If the participant received an initial dose of 120 mg, a 60 mg supplemental dose will be used. If drug supply does not permit availability of 60 mg capsules, a reduced supplemental dose of 40 mg may be administered following the 120 mg initial dose.

Table 7: Schedule of Procedures for Experimental Sessions

Approximate Time during an 8 hour session	Procedure or Action
9:30	Urine drug screen and pregnancy test, concomitant medication information
	collected, participant acclimated to environment, C-SSRS. Begin video
	recording.

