10.3.3 Follow-up Requirements

Details of all pregnancies in study participants and their partners will be collected after Enrollment (Visit 0) and collected through 10 days after the last Experimental Session. Pregnancies should be reported to the sponsor via telephone or email within 24 hours of site staff awareness.

In the event of a pregnancy, the participant will discontinue Experimental Sessions but may continue with non-drug Integrative Sessions, PCL-5 assessments, and Study Termination procedures. At a minimum, prior to withdrawal from the study, efforts should be made to assess the final PCL-5 immediately and complete Study Termination procedures.

The investigator will collect follow-up information on the participant or their partner and neonate and forward to the sponsor until the outcome of the pregnancy, which will be reported on an optional Pregnancy eCRF. Any termination, elective or spontaneous, will be reported. Abnormal pregnancy outcomes, such as spontaneous abortion, fetal death, stillbirth, congenital abnormalities, or ectopic pregnancy, will be reported as SAEs.

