11.3 Prohibited Medications

There are medications that should be discontinued prior to enrolling in the study. These medications should not be restarted until study termination unless previously discussed with the MPBC medical monitor.

To be enrolled in the study, participants must:

- Refrain from the use of any psychoactive medication not approved by the research team from Baseline through Study Termination (with the exception of gabapentin or certain opioids for pain control).
- Agree to follow an appropriate tapering initiated at enrollment visit, defined by the treating physician, and to respect a subsequent washout period of 5 half-lives of the medication (calculation based on parent or active metabolite half-life, whichever is longer) preceding Visit 3.
 - o For specific medications, including antidepressants and most antipsychotics, refer to the Allowed and Prohibited Medication List (if a drug is not in the list, it will be discussed with the Medical Monitor).
 - For non-selective irreversible MAOIs, a 2-week washout period following the taper is required (three weeks in the case of imipramine and clomipramine, tricyclic antidepressants with MAOI activity) prior to Experimental Session.

Use of St. John's Wort, and other herbs and medicines with notable serotonergic effects are prohibited from Baseline to Study Termination.

Ketamine must be discontinued 1 month prior to Preparatory Session 3 (Visit 3) and is prohibited until Study Termination.

If an SSRI, SNRI, MAOI (including non-psychiatric medications with MAOI activity, e.g. rasagiline, selegiline, linezolid), or other antidepressant (including antipsychotics used for depression, e.g. clozapine, risperidone, aripiprazole, ziprasidone, olanzapine) is used between Experimental Session 1 (Visit 4) and Study Termination (Visit 16), the participant will be withdrawn from treatment and continue in follow-up.

Opioids other than hydrocodone, morphine, and codeine are prohibited from Enrollment Confirmation to Study Termination. Participants taking prohibited opioids will be cross-tapered to an allowable opioid during the Preparatory Period.

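### Protocol 4.4.4 and 7.4 time the Visit 16 outcomes differently for participants who stop treatment but stay in the study; Visit 16 has no date without Session 3, and the SAP has no rule for an off-schedule form

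*Protocol*

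**What the plan says.** Protocol 4.4.4 (Early Termination from the Study) defines a Post-Treatment Early Termination as someone who stops study treatment but goes on with the primary and secondary outcome assessments. For this group: "Data collection will continue on the same schedule as planned through Study Termination visit procedures".

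Protocol 7.4 (Study Termination) places Visit 16 at 24 to 32 days after Experimental Session 3 (Visit 12), then adds: "Participants who have withdrawn from treatment but have continued for follow-up will also complete this assessment immediately upon withdrawal". It closes with: "After all Study Termination measures and assessments are completed, the participant is considered terminated from the study".

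Other sections bear on the same people:

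- Protocol 11.3 gives one route into the group. After use of specified medications between Visits 4 and 16, "the participant will be withdrawn from treatment and continue in follow-up".
- Protocol 10.3.3, on pregnancy, lets the participant continue with PCL-5 assessments and Study Termination procedures, and adds: "At a minimum, prior to withdrawal from the study, efforts should be made to assess the final PCL-5 immediately and complete Study Termination procedures".
- Protocol 10.1.7 asks, where possible, for final-visit procedures within 30 days of the last dose when a participant is withdrawn.

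None of these sections refers to the others on timing.

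The SAP names the group in section 1.0 (Post-dosing Early Terminators) without giving any timing. Section 8.2 covers safety-set inclusion and partial dates for adverse events and medications. Section 8.7.1 plans an MMRM of the PCL-5 from Visit 3 through Visit 16, and 8.7.2 treats the SDS similarly.

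**The concern.** Both the primary objective (PCL-5) and the key secondary objective (SDS) are changes from Visit 3 to Visit 16, so what counts as Visit 16 fixes the time point being estimated. For participants who stop treatment early, the protocol gives two answers: the planned date, or the day of withdrawal. Sites could reasonably follow either.

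If 7.4 is followed as written, a PCL-5 completed at withdrawal may be analysed as the Visit 16 value. The participant may also be closed out before the planned endpoint, and before the Integrative Sessions that 4.4.4 retains for those who develop certain exclusion criteria.

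The PCL-5 has some protection, because forms are also scheduled at Visits 6, 10 and 14. The SDS has none: Table 6 of the protocol schedules it only at Visits 3 and 16, so an at-withdrawal form could be the participant's only post-baseline value.

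These participants are meant to count. Protocol 8.4 seeks complete data from those who discontinue treatment, and places anyone with one dose and one follow-up assessment in the primary effectiveness analysis.

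**Working it through.** The plan states no figure on this point, so there is none to reproduce. The check compares the two timing rules using the protocol's own visit windows.

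**Inputs**

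- i1, Session 1 to Session 2: 21 to 56 days (Protocol 7.3.1)
- i2, Session 2 to Session 3: 21 to 56 days (Protocol 7.3.1)
- w, Session 3 to Visit 16: 24 to 32 days (Protocol 7.4; the same window is in SAP Table 2)
- d, days from the last session to withdrawal, taken as no later than the day the next session would have occurred

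**Step 1. Where the planned schedule would put Visit 16.** Without Session 3 the only anchor is missing, so the date has to be projected.

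- Stop after Session 1: i1 + i2 + w = 21 + 21 + 24 = 66 to 56 + 56 + 32 = 144 days after Session 1, a spread of 144 − 66 = 78 days.
- Stop after Session 2: i2 + w = 21 + 24 = 45 to 56 + 32 = 88 days after Session 2, a spread of 88 − 45 = 43 days.
- Session 3 received: 24 to 32 days after it, a spread of 8 days.

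Reading 4.4.4 as a projected date therefore does not fix a visit date.

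**Step 2. How far an at-withdrawal form falls before that date.**

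| Treatment stops | Gap | Minimum | Maximum |
|---|---|---|---|
| Between Sessions 1 and 2 | (i1 − d) + i2 + w | d = i1: 21 + 24 = 45 days | d = 0: 144 days |
| Between Sessions 2 and 3 | (i2 − d) + w | d = i2: 24 days | d = 0: 88 days |

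After Session 3 the planned visit is dated and the gap is at most 32 days, but the conflict between immediate and planned timing remains.

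**Step 3. The 30-day rule in 10.1.7.** If it were applied to this group, a form at day 30 would fall 66 − 30 = 36 to 144 − 30 = 114 days before the projected Visit 16 after Session 1, and 45 − 30 = 15 to 88 − 30 = 58 days before it after Session 2. It is a third timing, not a reconciliation of the other two.

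**Step 4. Recall.** The PCL-5 asks about the last 2 weeks (Protocol 6.1.1). A form completed less than 14 days after a session reaches back to before that session.

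**Step 5. Effect on the Visit 16 mean, by assumption only.** The documents give neither the share of participants who stop nor the score difference between the two forms. In a simple mean, shift = share × difference. With an assumed 5% to 20% affected and a difference of 5 to 20 points, this runs from 0.05 × 5 = 0.25 to 0.20 × 20 = 4.0 PCL-5 points. Borrowing the 7.5% dropout rate of the earlier Phase 2 studies (Protocol 1.2.4) as the share, with an assumed 10 points, gives 0.075 × 10 = 0.75. These are illustrations, not estimates.

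**The case against.** The strongest reply is that 7.4 speaks of people continuing in follow-up who will *also* complete the assessment. That can mean an extra form at withdrawal on top of the scheduled one, which is compatible with 4.4.4. Alternatively, withdrawal could mean later departure from follow-up, and 10.3.3 can be read that way. The first reading is possible, but it leaves two Study Termination records with nothing to say which is Visit 16, and the first of them ends participation under the closing sentence of 7.4. The second sits poorly with a sentence whose stated subject is withdrawal from treatment.

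A second reply is that Visit 16 is not wholly undated, since 10.1.7 ties final-visit procedures to the last dose. That rule is mainly about leaving the study. It applies only when possible, and neither 4.4.4 nor 7.4 refers to it. It is fair to say that some timing exists; it is the Visit 16 window itself that has no anchor without Session 3.

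A third reply is that the gaps are calendar distances to a date no passage tells sites to project, and that 144 days needs withdrawal on the day of Session 1 with every window at its maximum. This stands. The ranges show how far apart the two rules can be, not a bias. The study is also single-arm with no power calculation, and the scheduled PCL-5 forms before withdrawal still inform the MMRM.

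**Conclusion.** The point holds. The two sections give different timings for the same participants, Visit 16 has no anchor without Session 3, and the SAP does not say how an off-schedule PCL-5 or SDS form enters the analysis. The forms can differ in time by 45 to 144 days (stopping between Sessions 1 and 2) or 24 to 88 days (between Sessions 2 and 3), assuming the protocol's windows are kept and withdrawal comes no later than the next session's date.

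The size and direction of any effect on the Visit 16 means cannot be determined from the documents. It is probably modest for the PCL-5. For the SDS, the labelling of a single form can decide whether an early stopper has a post-baseline value at all. This should be corrected, but it does not undermine the study.

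**What to change.** 1. Reconcile Protocol 4.4.4 and 7.4 to one timing for outcome assessments after treatment stops, and cross-refer 10.1.7 and 10.3.3.
2. State when Visit 16 is due if Visit 12 did not take place, and collect the PCL-5 and SDS then.
3. Record any PCL-5 or SDS completed at withdrawal under a separate Early Termination label, not as Visit 16, and make clear that completing it does not end participation for someone who stays in follow-up.
4. Add an SAP paragraph on how that record enters the MMRM: for example, assigned by actual day, with a sensitivity analysis that uses it as the endpoint. Word any visit window so that slightly late Visit 16 forms from completers are not excluded.

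The cost is one protocol clarification, one visit label in the data-capture system and one SAP paragraph. Participants who stop early may complete one further set of outcome forms; if the whole Visit 16 is repeated, Protocol Table 1 allots it 2 hours. The documents do not say how many participants this would involve.

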7.4.1 Extension Studies

Upon completion of the study, defined as completing at least one Experimental Session and one PCL-5 assessment beyond Baseline and terminating participation, participants will be asked to join the LTFU extension study to observe long-term effects. This study will not involve any additional Experimental Sessions or administration of IMP. The ICF for this study will be provided to eligible participants at the Study Termination visit if available. This study will measure outcomes at least 6 months after the last Experimental Session.

Any sub-studies will be detailed in separate documents.

7.4.2 Exit Plan/Plan for Moving Forward

At Study Termination, participants will be provided with an Exit Plan/Plan for Moving Forward. This Exit Plan/Plan for Moving Forward will summarize treatments completed, current medications, and

contact information for more information about the study if needed. Participants may request a referral for further therapeutic or medical care if appropriate. Enrolled participants who terminate the study early will be provided an Exit Plan/Plan for Moving Forward at their last contact. Screen Failures will be provided a referral if requested.

8.0 Investigational Product

8.1 Description of Active Compounds

The Active Pharmaceutical Ingredient (API) to be used in this protocol is MDMA (as hydrochloride salt [HCl]). This ring-substituted phenethylamine has a complex pharmacology, but it acts most prominently as a monoamine releaser and re-uptake inhibitor. Its direct actions on serotonergic, adrenergic, and other receptors are considerably lower. Refer to the IB for a comprehensive review of the pharmacology, effects and proposed mechanisms of action of the IMP. The IMP will be compounded with inactive excipients such as mannitol and magnesium stearate.

Table 8: Study Medication Intervention(s) Administered

Intervention Label	Active Intervention
Intervention Name	3,4-methylenedioxymethamphetamine (MDMA) as a hydrochloride salt (HCl)
Intervention Description	Initial doses (per Experimental Session) include 80 mg or 120 mg MDMA HCl,
_	followed 1.5 to 2 hours later by a supplemental dose of 40 mg or 60 mg MDMA
	HCl.
Type	Drug
Dose Formulation	hydroxypropylmethylcellulose (HPMC) capsule
Unit Dose Strength(s)	40 mg or 60 mg MDMA HCl
Dosage Level(s)	Initial dead, 90 mg MDMA LICI for first accion and 90 mg or 120 mg MDMA
Dosage Level(s)	Initial dose: 80 mg MDMA HCl for first session and 80 mg or 120 mg MDMA HCl for following sessions
	HCI for following sessions
	Cumplemental descriptions on (0 mg MDMA HCl
	Supplemental dose: 40 mg or 60 mg MDMA HCl
Inactive Ingredients	Mannitol and magnesium stearate
Route of Administration	Oral
Use	Experimental
IMP and NIMP/AxMP.	IMP
Sourcing	Provided centrally by the sponsor
Packaging and Labeling	Study intervention will be provided in an open-label container. Each container
	will be labeled as required per country and federal, state, and local regulations.
	This will include the following:
	J
	Caution: New Drug – Limited by Federal (or United States) law to
	investigational use.
	investigational asc.

8.1.1 Doses

This study will explore the effectiveness of three Experimental Sessions of therapy assisted by flexible doses of MDMA. Initial doses per Experimental Session include 80 mg or 120 mg MDMA HCl compounded with mannitol and magnesium stearate, followed 1.5 to 2 hours later by a supplemental dose (40 mg or 60 mg MDMA HCl). If the participant received an initial dose of 80 mg, a 40 mg supplemental dose will be used. If the participant received an initial dose of 120 mg, a 60 mg supplemental dose will be used. If drug supply does not permit availability of 60 mg capsules, a reduced supplemental dose of 40 mg may be administered following the 120 mg initial dose. Total amounts of MDMA HCl to be

administered per Experimental Session range from 80 mg to 180 mg. All drug is encapsulated with hydroxypropyl methylcellulose (HPMC) capsules.

Refer to Table 3: Dose Regimen of MDMA.

8.1.2 Dose Modifications

A participant will receive a divided-dose of 120 mg or 180 mg per Experimental Session. In the first Experimental Session, the initial dose will be 80 mg MDMA HCl. In the second and third Experimental Sessions, the initial dose may be increased to 120 mg MDMA HCl unless tolerability issues emerge with the first dose or it is refused by the participant. The choice of whether to keep the dose the same or change it from the first Experimental Session will be made by the therapy pair the in consultation with the site physician based on observed response, tolerability to the previously administered dose, and discussion with the participant. In each Experimental Session, 1.5 to 2 hours after the initial dose is given, the participant will be administered a supplemental dose unless tolerability issues emerge with the first dose or it is refused by the participant. If an AE requiring medical attention occurs between the initial and supplemental dose this will be evaluated as a potential tolerability issue by the site physician. If a participant prefers not to take the supplemental dose, the reason will be documented. If the participant received an initial dose of 80 mg, a 40 mg supplemental dose will be used. If the participant received an initial dose of 120 mg, a 60 mg supplemental dose will be used. If drug supply does not permit availability of 60 mg capsules, a reduced supplemental dose of 40 mg may be administered following the 120 mg initial dose.

